6.1.1 Guidelines for Dabrafenib Dose Modification and Treatment of Adverse Events

The severity of adverse events will be graded utilizing the Common Terminology Criteria for Adverse Events Version 4.0 (CTCAE v4.0). Dose modifications of Dabrafenib will be made according to the dose levels outlined in **Table 1**.

Table 1. Dabrafenib Dose Levels

| Dose Level | Dabrafenib Dose/Schedule |
|-------------------|---------------------------------|
| 0 | 150 mg BID |
| - 1 | 100 mg BID |
| - 2 | 75 mg BID |
| - 3 | 50 mg BID |

Guidelines for dose modifications and interruptions for management of toxicities associated with the study treatment other than those pertaining to neutropenia, fever, rash, hand foot skin reactions (HFSR), renal insufficiency, liver chemistry abnormalities, left ventricular ejection fraction (LVEF) are provided in **Table 2**.

Dose modifications specifically for neutropenia are outlined in **Table 3**. Prophylactic antibiotics are recommended for treatment of neutropenic fever (defined as a single fever $>38.3^{\circ}\text{C}$ (101°F), or a sustained temperature $>38^{\circ}\text{C}$ (100.4°F) for more than one hour in a patient with absolute neutrophil count (ANC) <500 cells/microL, or <1000 cells/microL with a predicted nadir of <500 cells/microL). The choice of antibiotic for neutropenic fever is per the treating physician and the institution's hospital policy.

Dose modifications for fever are provided in **Table 4**. Antipyretic use is permitted for symptomatic relief of fever. In the absence of severe neutropenia, the use of antibiotics is at the clinical discretion of the examining physician/investigator. For complicated fever, defined as Grade ≥ 3 fever or any grade with signs and symptoms including; rigors, dehydration, hypotension, dizziness or weakness, the administration of both Dabrafenib and Trametinib should be interrupted/held.

Dose modifications for rash and general recommendations for rash management are provided in **Table 5**.

Dose modifications for hand foot skin reaction (HFSR) are provided in **Table 6**. Treatment of squamous cell carcinoma (SCC), keratoacanthoma (KA), and actinic keratosis (AK) lesions should be based upon institutional practice. Dose interruptions or modifications are usually not required for SCC/KA. Biopsies of any new skin lesions suspicious for malignancy and pre-malignancy (SCC, AK, KA) are recommended.

Dose modifications for renal insufficiency are outlined in **Table 7**.

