Table 2. Dose Modification Table for Toxicities Other Than **Neutropenia, Fever, Rash, HFSR, LVEF, renal insufficiency or liver chemistry abnormalities

| Non-hematologic and hematologic Toxicity (except**) | Dose Modification Algorithms ^{a, b, d, e} |
|---|---|
| Grade 1 | Continue Dabrafenib at full dose, monitor as clinically indicated. |
| Grade 2 | 
For Grade 2 Diarrhea with accompanying risk factors^c Hold Dabrafenib until return to \leq Grade 1, provide supportive care.
 
All other toxicities: Consider holding Dabrafenib until resolution to Grade 1 or baseline; provide supportive care as clinically indicated. Monitoring of laboratory values should occur as clinically indicated.
 
For Grade 2 or higher respiratory symptoms (i.e. cough, dyspnea, hypoxia etc.), evaluation by a CT scan is recommended.
 |
| Grade 3 | 
For Grade 3 toxicity, hold Dabrafenib until toxicity is Grade 1 or baseline then reduce dose of Dabrafenib by 1 dose level. The subject may be continued at the same dose if, in the judgment of the investigator, the toxicity is considered to be unrelated to Dabrafenib. Continue to monitor as clinically indicated.
 
If any Grade 3 toxicity recurs, hold dosing until Grade 1 or baseline, then reduce current dose of Dabrafenib by one dose level.
 |
| Grade 4 | 
Discontinue Dabrafenib. Continue to monitor as clinically indicated, and provide supportive care as needed
 
If in the investigator's judgment the toxicity is unlikely to recur then, hold until toxicity is Grade 1 or baseline, then reduce dose of Dabrafenib by 1 dose level. If Grade 4 toxicity recurs after dose reduction, discuss continuation of study drug with the PI.
 |

** Neutropenia, Fever, Rash, HFSR, LVEF, renal insufficiency or liver chemistry abnormalities

- The minimum dose is 50 mg BID. If a subject requires dose reduction below 50 mg BID then the subject must be discontinued from study medication.
- For adverse events of abdominal pain or suspected pancreatitis, amylase and lipase laboratory samples should be collected.
- Risk factors for cancer treatment-induced diarrhea include: fever, orthostatic symptoms (i.e. dizziness), abdominal pain/cramping, or weakness.
- If the patient has a Grade 3 or 4 laboratory abnormality, that in the judgment of the investigator, is not considered clinically significant, dose modification is not required.

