6.1.2.2 Left Ventricular Ejection Fraction (LVEF) Stopping Criteria

ECHO or MUGA must be performed at baseline and at follow-up visit(s) per the schedule in the Study Calendar. Subjects who have an asymptomatic, absolute decrease of > 10% in LVEF compared to baseline and the ejection fraction is below the institution's lower limit of normal (LLN) should temporarily discontinue Dabrafenib and have a repeat evaluation of LVEF within 1 week. ECHO or MUGA should be repeated every 1-2 weeks for 4 weeks or until LVEF recovery to above institutional lower limit of normal and within 10% of baseline

If the LVEF recovers (defined as \geq LLN and absolute decrease \leq 10% compared to baseline) at any time during the next 4 weeks, the subject may be restarted on Dabrafenib at reduced dose level, after consultation and approval of the Protocol Chair. For such subjects, monitoring of LVEF will then be performed 2 and 4 weeks after rechallenge, and every 4 weeks thereafter for 12 weeks and then per protocol.

If repeat LVEF does not recover within 4 weeks, then the subject should permanently discontinue Dabrafenib. Ejection fraction should continue to be monitored every 4 weeks for 16 weeks or until resolution.

Subjects with a Grade 3 or 4 (symptomatic) left ventricular systolic dysfunction must discontinue Dabrafenib. Ejection fraction should continue to be monitored every 4 weeks for 16 weeks or until resolution. If recovery occurs (LVEF to above institutional LLN and symptom resolution) within 4 weeks, the subject may restart Dabrafenib at a reduced dose after consultation and approval of the Protocol Chair.

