6.1.2.4 QTc Stopping Criteria

If QTc corrected (QTcB) is greater than or equal to 530 milliseconds¹, the study drug Dabrafenib will be held.

¹ If ECG demonstrates greater than 500 millisecond QTc (grade 3 or 4), obtain 2 more ECGs over a brief period, and then use the averaged QTc values of the 3 ECGs to determine if averaged QTc greater than or equal to 530 millisecond. If that is the case, the subjects should have study medication withheld.

If the QTc prolongation resolves to Grade 1 or baseline, the subject may be restarted on the study medication if after the Protocol Chair agrees that the subject will benefit from further treatment.

6.2 Trametinib Delays/Modifications (applicable to patients on ARM B):

Given that there are several overlapping AEs between Dabrafenib and Trametinib, dose modification/stopping guidelines for all patients on ARM B must follow guidelines for Dabrafenib. In each of those categories, dose reduction, dose holding or dose continuation of Trametinib must follow similar criteria as for Dabrafenib. If there is discrepancy between two guidelines for a given AE, please follow guidelines for Dabrafenib for patients on ARM B. Diarrheas, peripheral/periorbital edema, acneiform rash, please follow guidelines given in section 6.2.

Table 8. Trametinib Dose Levels

| Dose Level | Trametinib Dose |
|-------------------|------------------------|
| 0 | 2 mg once a day |
| - 1 | 1.5 mg once a day |
| - 2 | 1 mg once a day |

A maximum of two Trametinib dose level reductions are allowed. If a third dose level reduction is required, treatment will be permanently discontinued. If a dose reduction of Trametinib is required, but the toxicity resolves and no additional toxicities are seen after two cycles of treatment, the dose of Trametinib may be re-escalated but should not exceed 2 mg once a day.

Trametinib dose modification guidelines are outlined in Table 9 for clinically significant toxicities that are deemed related to Trametinib (i.e. peripheral and periorbital edema).

Dose modification guidelines for rash are outlined in Table 10.

Table 9. Dose Delay and Modification for Trametinib related AEs (for peripheral edema, periorbital edema)

| Toxicity Grade^a | Dose Modification of Trametinib |
|-----------------------------------|--|
| Grade 1 | Continue at current dose level. |

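### Table 2's exception list omits squamous cell carcinoma and keratoacanthoma (SCC/KA), so a related grade 3 case must be held and dose-reduced although Section 6.1.1 says this is not usually needed

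*Combined protocol and SAP*

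**What the plan says.** Section 6.1.1 sends all toxicities to Table 2 except seven: neutropenia, fever, rash, hand-foot skin reaction, renal insufficiency, liver chemistry abnormalities and LVEF. The section text, the Table 2 title and the table's ** footnote all name the same seven. SCC/KA appears in none of them.

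The grade 3 row of Table 2 reads: "For Grade 3 toxicity, hold Dabrafenib until toxicity is Grade 1 or baseline then reduce dose of Dabrafenib by 1 dose level". It allows one exception tied to causality: "The subject may be continued at the same dose if, in the judgment of the investigator, the toxicity is considered to be unrelated to Dabrafenib". Footnote d allows another, for laboratory abnormalities that the investigator judges not clinically significant.

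Shortly before Table 2, the text of Section 6.1.1 leaves treatment of SCC, KA and actinic keratosis to institutional practice and then says: "Dose interruptions or modifications are usually not required for SCC/KA". That sentence carries no grade limit.

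For Arm B, Section 6.2 says that "dose reduction, dose holding or dose continuation of Trametinib must follow similar criteria as for Dabrafenib". It also ranks the dabrafenib guideline above the trametinib guideline when the two differ. It does not rank event-specific text against Table 2.

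**The concern.** For a related grade 3 SCC/KA, two instructions in one subsection point different ways. Table 2 makes a hold and a one-level reduction the required action. The text calls the same steps unnecessary in the usual case. A site that works from the table will cut the dose; a site that works from the text will generally leave it alone.

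At stake are consistent handling of a known dabrafenib effect, avoidable loss of dose in individual patients, and the meaning of one descriptive summary. Section 13.4 assesses tolerability partly by counting patients who needed dose modifications or delays, and explores differences between arms. Some of that count would reflect which sentence a site followed. Section 7.3 says skin cancers such as keratoacanthoma are generally less common on the combination, so the extra modifications would tend to fall on Arm A.

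**Working it through.** The plan gives no figure to reproduce. The check compares the texts and then sizes the event.

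**1. Does Table 2 reach SCC/KA?** It covers hematologic and non-hematologic toxicity apart from the seven named items. SCC/KA is a treatment-related event in Table 11 and is not one of the seven, so it is covered.

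**2. Does either exception in Table 2 release it?** The causality exception needs the event to be judged unrelated, so a related SCC/KA stays in. Footnote d concerns laboratory abnormalities, and a skin tumor is not one.

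**3. The two actions for a related grade 3 SCC/KA**

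| | Table 2, grade 3 row | Section 6.1.1 text |
|---|---|---|
| Dabrafenib hold | Yes, to grade 1 or baseline | Usually none |
| Dabrafenib dose from level 0 | 150 to 100 mg twice daily | Usually unchanged |
| Trametinib on Arm B, if it follows | 2 to 1.5 mg daily | Usually unchanged |

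Dose steps (Tables 1 and 8):
- dabrafenib: (150 − 100)/150 = 33%
- trametinib: (2 − 1.5)/2 = 25%. Section 6.2 allows re-escalation after two cycles if the toxicity resolves and no other appears, so this cut need not be permanent.

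**4. How often could it happen?** The documents give no rate of related grade 3 SCC/KA in thyroid cancer. Each line below assumes that a rate from another population carries over to 26 patients per arm.

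- First-in-human study (Section 2.3.5.2; 184 subjects, mixed doses, not attributed): SCC is listed first among grade 3 or 4 events seen in at least 4%. At the 4% floor, 26 × 0.04 = 1.04, or about 1 patient on Arm A.
- Phase II monotherapy study at 150 mg twice daily (same section; 92 subjects): grade 3 SCC in more than one subject, so at least 2/92 = 2.2%. Then 26 × 2/92 = 0.57 patients as a floor.
- Loose ceilings: related SCC of any grade is in the band below 10% in Table 11, so under 26 × 0.10 = 2.6 patients. The first-in-human rate of SCC as a serious event was 11%, giving 26 × 0.11 = 2.86. Neither measures related grade 3 SCC.
- Lower end: 0.

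Arm B: Table 13 puts SCC/KA in the same 1% to 10% band, but with the statement in Section 7.3 the number is probably smaller than on Arm A.

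**The case against.** The strongest reply is that the two texts can be read together. The SCC/KA sentence states a general expectation across grades and does not order anyone to continue. A site that holds drug for a related grade 3 lesion therefore breaks no rule. Section 6.1.1 introduces Table 2 as guidelines, the SCC/KA sentence stands close before it, and reading specific text over a catch-all table is natural. Part of this stands: the word usually leaves discretion, and many sites would resolve the matter sensibly. But no sentence says that the specific text prevails. The protocol also took the trouble to list exceptions, so a careful reader may conclude that anything unlisted stays under the table. Table 2 still requires what the text calls usually unnecessary.

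A reader might infer a second conflict of the same kind for QTc. Section 6.1.2.4 has a footnote: "If ECG demonstrates greater than 500 millisecond QTc (grade 3 or 4), obtain 2 more ECGs over a brief period". The site must then "use the averaged QTc values of the 3 ECGs to determine if averaged QTc greater than or equal to 530 millisecond", and drug is withheld only if so. For a related event with an average above 500 and below 530 ms, a 30 ms window, Table 2 requires action and Section 6.1.2.4 does not. The documents do not support calling this a contradiction. Section 6.1.2.4 is a stopping rule. It says when drug must be held and never says to continue below 530 ms, so holding and reducing under Table 2 breaches nothing in it. Nor is a restart dose plainly missing. Section 6.1.2.4 says "If the QTc prolongation resolves to Grade 1 or baseline, the subject may be restarted on the study medication" without naming a dose, whereas the LVEF rule says "the subject may be restarted on Dabrafenib at reduced dose level". As the text stands, however, the grade 3 row of Table 2 supplies a one-level reduction. The gap would open only if QTc were exempted.

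Valvular toxicity is also absent from the list. Section 6.1.2.3 is stricter than Table 2, so following it satisfies both.

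**Conclusion.** The point holds for SCC/KA and is minor. For a related grade 3 SCC/KA, Table 2 requires a hold and a 33% dabrafenib cut that the text of the same section calls usually unnecessary, and nothing ranks the two.

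The likely size is about 1 of 26 patients on Arm A and probably fewer on Arm B. This assumes that the first-in-human rate, from mixed doses and without attribution, carries over to thyroid cancer at its 4% floor. The true number could be 0, and the loose ceilings stay below 3 per arm.

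The effect is inconsistent or unneeded dose cuts in those patients and some distortion of the descriptive dose-modification count in Section 13.4. A reader might infer that lost dose threatens the response comparison. The documents give nothing to support that: no effect on the primary endpoint, sample size or power is claimed.

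For QTc the documents support only a question about what the sponsor intends between 500 and 530 ms. No frequency is given for that event, and QTc prolongation appears in none of Tables 11 to 13.

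**What to change.** Add SCC/KA to the exceptions in three places: the Section 6.1.1 text, the Table 2 title and the ** footnote. The cost is wording only, with no added procedures or patients. The effect on care is that a related grade 3 SCC/KA passes from a required hold and reduction to the investigator's judgment, which is what the Section 6.1.1 text already describes.

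Do not exempt QTc by default, and do not add a blanket sentence that event-specific rules override Table 2. Either step would drop the more protective reading for an averaged QTc that the protocol itself labels grade 3 or 4, and would remove the restart dose that Table 2 now supplies. That is a safety trade-off for the sponsor to decide.

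Instead, ask the sponsor to state the intended action for a related averaged QTc above 500 and below 530 ms. If QTc is later exempted from Table 2, Section 6.1.2.4 should state a restart dose. The valve rule needs no change.

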- For subjects who develop symptoms associated with uveitis including blurry vision, eye pain or erythema ophthalmologic consult is required.

Table 3. Dose Modification Table for Neutropenia

| Grade | ANC value /mm3 | Management of Neutropenia | Dabrafenib Dose Adjustment |
|-------|----------------|---|---|
| 1 | 1500-LLN | 
 Monitor per protocol time and events table | Continue at current dose |
| 2 | 1000-<1500 | 
 Re-check ANC in 1 week. If improvement to grade 1, continue to monitor per protocol time and events table. If stable at grade 2, monitor ANC every 2 weeks until resolution to grade 1 or until stable for 4 weeks If worsens to grade 3 or 4 follow below. | Any occurrence: continue at current dose |
| 3 | 500-<1000 | 
 Re-check ANC at least weekly during dose interruption. If resolved to grade 1, re-check ANC 3 days after rechallenge with Dabrafenib and then 1 week later. | 
 Any occurrence: hold until return to grade 1, then reduce one dose level 1st recurrence: Discontinue Dabrafenib or hold until return to grade 1, then reduce one dose level 2nd recurrence: Discontinue Dabrafenib. |
| 4 | <500 | 
 Re-check ANC at least weekly If resolved to grade 1, re-check ANC 3 days after rechallenge with Dabrafenib and then 1 week later. | 
 Discontinue or hold until return to grade 1, then reduce Dabrafenib by one dose level. 1st recurrence: discontinue Dabrafenib. |

Table 4. Dose Adjustments for Fever (Pyrexia) ^{a, b}

| Occurrence | Management | Study drug adjustment |
|-----------------------------|---|---|
| 1st event | 
 • Clinical evaluation for infection and hypersensitivity^c • Laboratory work-up^c • Hydration as required^d | 
 • Administer anti-pyretic treatment if clinically indicated^e • Continue or Interrupt dabrafenib depending on severity of pyrexia and associated conditions-for example, if fever was associated with dehydration, hypotension, or renal insufficiency, hold dabrafenib and reduce dabrafenib by one dose level when restarted. • Once pyrexia resolves to baseline, restart dabrafenib at the same dose if dabrafenib was held. |

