| 2nd event | 
 • Work-up at physicians' discretion | 
 • Same as for 1st event and: 
 • Administer anti-pyretic treatment if clinically indicated^f • Consider oral corticosteroids (i.e., prednisone 10 mg/d) for at least 5 days or as clinically indicated^f |
| Subsequent events | 
 • Work-up at physicians' discretion | 
 • Same as for 1st event and: 
 • Administer anti-pyretic treatment if clinically indicated^e • Optimize oral corticosteroid dose as clinically indicated for recalcitrant pyrexia^f • If corticosteroids have been tapered and pyrexia recurs, restart steroids • If corticosteroids cannot be tapered or escalating doses are required, consult protocol chair. • If associated with dehydration, hypotension or renal insufficiency (on 2 or more occasions), reduce dabrafenib by one dose level |

BUN = blood urea nitrogen;

a. Fever (pyrexia) is defined as a body temperature equal to or above 38.5° Celsius or 101.3° Fahrenheit.

- b. For subjects experiencing fever (pyrexia) complicated by rigors, severe chills, etc., a clinical evaluation is mandatory for each event; anti-pyretic treatment should be started immediately at the first occurrence and prophylactic anti-pyretic treatment is recommended
- c. Thorough clinical history for symptoms of infection or hypersensitivity is required; laboratory work-up may include complete-blood-count, electrolytes, creatinine, BUN, liver-function tests, blood culture, and urine culture.
- d. Oral hydration should be encouraged in subjects without evidence of dehydration. Intravenous hydration is recommended in subjects experiencing pyrexia complicated by dehydration/hypotension.
- e. Anti-pyretic treatment may include acetaminophen (paracetamol), ibuprofen, or suitable anti-pyretic medication according to institutional standards. Prophylactic anti-pyretic treatment may be discontinued after three days in the absence of pyrexia
- f. In subject experiencing pyrexia complicated by rigors, severe chills, etc., which cannot be controlled with anti-pyretic medication, oral corticosteroids should be started at the 2nd event and prednisone doses should be gradually increased for subsequent events.

Table 5. Dose Modification for Skin Rash

| Skin Toxicity Grade (CTCAE v 4.0) | Guideline for Management | Dose Reduction^a |

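### Table 4 gives two dabrafenib restart doses after a first fever with dehydration, hypotension or renal insufficiency, and Table 7 adds a third instruction when the kidney is involved

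*Combined protocol and SAP*

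**What the plan says.** All the relevant text is in Section 6.1.1 (dabrafenib) and Section 6.2 (trametinib).

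- **Table 4, first event, dose column, second bullet.** It leaves continuing or interrupting to the severity of the fever, then gives a specific case: "if fever was associated with dehydration, hypotension, or renal insufficiency, hold dabrafenib and reduce dabrafenib by one dose level when restarted".
- **Table 4, first event, third bullet.** "Once pyrexia resolves to baseline, restart dabrafenib at the same dose if dabrafenib was held".
- **Table 4, second and subsequent events.** Both rows open with "Same as for 1st event and". The subsequent-events row also contains this line: "If associated with dehydration, hypotension or renal insufficiency (on 2 or more occasions), reduce dabrafenib by one dose level".
- **Section 6.1.1 text on complicated fever.** This covers Grade 3 or higher fever, or fever of any grade with "rigors, dehydration, hypotension, dizziness or weakness, the administration of both Dabrafenib and Trametinib should be interrupted/held". No restart dose is given there.
- **Table 7, second row.** Dabrafenib is interrupted for a creatinine rise above 0.5 mg/dL or a value above 2 mg/dL. Item 2 sends febrile patients to the pyrexia guidance. Item 5 lets the investigator choose the same dose or one level lower once creatinine is back to baseline.
- **Table 7, first row.** Dabrafenib continues for a rise above 0.2 and up to 0.5 mg/dL over baseline, with no limit on the absolute value.
- **Section 6.2, Arm B.** "dose reduction, dose holding or dose continuation of Trametinib must follow similar criteria as for Dabrafenib". The tie-break is: "If there is discrepancy between two guidelines for a given AE, please follow guidelines for Dabrafenib for patients on ARM B".

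**The concern.** The third bullet of the first-event cell depends only on whether dabrafenib was held. For the three named complications the second bullet itself requires a hold, so that condition is always met in exactly the patients for whom the second bullet requires a reduction. Followed literally, the cell returns a patient with complicated fever to full dose one line after telling the site not to.

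What is at stake is the dose given to an individual patient recovering from a complicated fever, and consistency between sites. Two compliant sites could restart the same patient at different doses. The Section 6.2 tie-break ranks dabrafenib guidance above trametinib guidance, so it cannot choose between two dabrafenib bullets, and in Arm B the uncertainty carries over to trametinib.

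**Working it through.** The plan gives no figure to reproduce. The check is to apply each instruction to the same patient and then test the Table 7 rows for overlap.

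**Step 1. First fever with one of the three complications, patient at 150 mg BID.** Dose levels are from Table 1 (150, 100, 75, 50 mg BID).

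| Instruction | Restart dose |
|---|---|
| Table 4, first event, second bullet | 100 mg BID |
| Table 4, first event, third bullet | 150 mg BID |
| Table 4, subsequent events, two-occasions line | implies no reduction at the first occasion: 150 mg BID |
| Section 6.1.1 text | hold; no restart dose |
| Table 7, second row, item 5 (if creatinine met that row) | 150 or 100 mg BID at discretion |

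Difference from the starting dose: (100 − 150)/150 = −33%. At lower levels the pairs are 75 or 100 mg, 50 or 75 mg, and discontinue or 50 mg BID.

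**Step 2. Arm B.** Table 8 levels are 2, 1.5 and 1 mg once daily. If trametinib steps with dabrafenib, the restart dose is 1.5 or 2 mg: (1.5 − 2)/2 = −25%.

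**Step 3. Do the later rows settle it?** No. They import the whole first-event cell, conflict included. The two-occasions line then makes the reduction conditional on repetition, which would be unnecessary if every such fever already lowered the dose.

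**Step 4. Table 7 overlap.** Let b be baseline creatinine and r the rise, in mg/dL. The first row applies when 0.2 < r ≤ 0.5. The second applies when r > 0.5 or b + r > 2.0. Both apply when 0.2 < r ≤ 0.5 and b + r > 2.0, which requires b > 2.0 − 0.5 = 1.5.

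- Example: b = 1.60 and r = 0.45 give 2.05, which meets both the continue row and the interrupt row.
- From b = 1.80 upward, every rise in the first row also meets the second, since 1.80 + 0.2 = 2.00.
- Section 3.1.9 admits creatinine up to 1.5 × the institutional upper limit of normal (ULN). The ULN in mg/dL is not given, so a range is assumed, with baseline taken to be within the eligibility limit:

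| Assumed ULN | Highest eligible baseline (1.5 × ULN) | Baselines with overlap |
|---|---|---|
| 0.9 | 1.35 | none |
| 1.0 | 1.50 | none |
| 1.1 | 1.65 | above 1.50 to 1.65 |
| 1.2 | 1.80 | above 1.50 to 1.80 |
| 1.3 | 1.95 | above 1.50 to 1.95 |

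The overlap therefore exists only where ULN exceeds 1.0 mg/dL.

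**The case against.** The best defence is that a specific rule overrides a general one. The second bullet names three complications; the third is the default for other holds. Such holds exist: the Section 6.1.1 text also interrupts treatment for Grade 3 or higher fever, rigors, dizziness or weakness, and the second bullet allows interruption on severity alone. On this reading the third bullet has its own patients and there is no contradiction.

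Much of this stands. It is the natural reading, and many sites would adopt it. It does not close the matter, because the third bullet is not worded as a default, the two-occasions line supports the opposite reading, and Table 7 item 5 allows discretion where Table 4 requires a reduction.

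It is also fair to say that resolving the text towards reduction at every such fever is a policy choice, which the documents do not show to be the intent. On Table 7, the absolute trigger in the second row works naturally as an override, and most clinicians would take the stricter row. That point is minor.

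A reader might try to put a number on this from the first-in-human study in Section 2.3.5.2, where 9% of 184 patients had dabrafenib interrupted for pyrexia. The documents do not support that step. The rate comes from monotherapy at doses from 12 mg QD to 300 mg BID, it counts all fever holds and not only complicated ones, and no fever-hold rate is given for the combination.

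**Conclusion.** The point holds as a wording fault in a dosing rule. One Table 4 cell contains two incompatible restart instructions for a first complicated fever, the rest of the table supports either reading, no precedence rule applies, and Table 7 adds a third answer for renal insufficiency. From the starting dose the gap is 100 against 150 mg BID for dabrafenib. It is 1.5 against 2 mg for trametinib in Arm B, if trametinib moves with dabrafenib. The number of patients affected is unknown.

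The Table 7 overlap is real but narrow: it needs a baseline above 1.5 mg/dL, which is eligible only if the institutional ULN exceeds 1.0 mg/dL, an assumption.

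A reader might also infer that the ambiguity biases the comparison of arms. Nothing in the documents shows this. The Section 13.1.3 rule compares observed response rates by randomised arm against a difference of 0.10 and does not depend on the restart dose, and no arm imbalance in outcome is shown. The issue is patient-level dosing safety and consistency between sites.

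**What to change.** Four short edits in an amendment, with no new visits or data:

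1. **Table 4, first event, third bullet.** Restrict it to dabrafenib held for fever without dehydration, hypotension or renal insufficiency.
2. **Table 4, subsequent events.** Remove the whole two-occasions line. The opening reference to the first-event rule already carries the reduction; deleting only the parenthesis would state it twice.
3. **Table 7, second row, item 5.** State that Table 4 governs the restart dose when renal insufficiency accompanies fever. Without this, edit 1 would leave a mandatory reduction in one table and discretion in the other.
4. **Table 7, first row (minor).** Add the condition that serum creatinine is at or below 2 mg/dL, so that the interrupt row governs above that value.

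If the sponsor intends a reduction only from the second complicated fever, the first-event cell should say so instead.

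The cost is clinical. Some patients restart one level lower than the same-dose reading allows, and repeated episodes add up. For trametinib, "A maximum of two Trametinib dose level reductions are allowed", and Section 6.2 ends treatment if a third is required; re-escalation is possible after two cycles free of further toxicity. For dabrafenib, three reductions lead from 150 to 50 mg BID, and a fourth would mean discontinuation. That floor is stated in a footnote to Table 2, which does not itself cover fever, but Table 1 has no lower level. The sponsor should accept this consequence knowingly.
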